5.1 Contraception requirements

As the reproductive toxicity studies are not yet final, highly effective contraception is proposed for all trials with CJM112 that include WOCBP, until further information is available. WOCBP, defined as all women physiologically capable of becoming pregnant, unless they are using highly effective methods of contraception during dosing and for 13 weeks (= 5 times the mean terminal half-life in psoriasis patients) after stopping CJM112.

Highly effective contraception methods include:

- Total abstinence (when this is in line with the preferred and usual lifestyle of the subject). Periodic abstinence (i.e., calendar, ovulation, symptothermal, postovulation methods) and withdrawal are not acceptable methods of contraception
- Female sterilization (have had surgical bilateral oophorectomy (with or without hysterectomy), total hysterectomy or tubal ligation at least 6 weeks before taking study treatment. In case of oophorectomy alone, only when the reproductive status of the woman has been confirmed by follow up hormone level assessment
- Male sterilization (at least 6 months prior to screening). The vasectomized male partner should be the sole partner for that subject
- Use of oral, injected or implanted hormonal methods of contraception or placement of an IUD or IUS or other forms of hormonal contraception that have comparable efficacy (failure rate <1%), for example hormone vaginal ring or transdermal hormone contraception.

In case of use of oral contraception women should have been stable on the same pill for a minimum of 3 months before taking study treatment.

5.2 Prohibited treatment

Table 5-1 Prohibited treatment

Medication/treatment	Action to be taken	Required wash-out (prior to randomization/first treatment)
Exposure to any IL-17 or IL-17R blocking agents	Do not include in the study/discontinue study treatment	Exclusion criterion
TNF α blockers such as adalimumab and infliximab	Discontinue study treatment	Wash-out: 3 months
IL-12 or IL-23 blocking agents such as briakinumab and ustekinumab, including investigational p19 antibodies	Discontinue study treatment	Wash-out: 6 months
Any biologics, other than above	Discontinue study treatment	Wash-out: 3 months or at least 5 times the half life
Any systemic immunosuppressant or immunomodulator, such as cyclosporine, methotrexate, cyclophosphamide, azathioprine, corticosteroids (includes local injections), etc.	Discontinue study treatment (unless local injections: to be discussed with sponsor on case by case basis)	Wash-out: 4 weeks
Any systemic treatment with antibiotics (longer than 2 weeks), in particular tetracyclines and/or macrolides, but as well other oral anti-acne treatment such as dapsoe and zinc. These treatments are accepted for periods shorter than 2 weeks, if medically indicated.	Discontinue study treatment if antibiotic treatment (not for acne) is longer than 2 weeks All other cases to be discussed with Sponsor on case by case basis	Wash-out: 4 weeks
Use of any systemic hormonal treatment (with the exception of hormonal contraceptive) (including anti-androgens, such as spironolactone, finasteride and cyproterone acetate) within 1 month before baseline.	To be discussed with sponsor on case by case basis	Wash-out of 1 month
Oral contraceptives can be continued if stable for the last 3 months before baseline if stable in dose and dosing regimen and type and if the patient plans to continue throughout the study.	To be discussed with sponsor on case by case basis	Wash out for change in dose, regimen or type: 3 months
Systemic retinoids, in particular isotretinoin	Discontinue study treatment	Wash-out: 6 months
Comedo extraction, electrocautery, and medical chemical peels using glycolic acid, salicylic acid, and trichloroacetic acid (for acne or acne lesions and /or done on areas of evaluation (face, back, chest, shoulder, etc.))	Discontinue study treatment for medium depth facial peels Sporadic local treatment to be discussed with sponsor on case by case basis	No wash-out Medium depth peels 3 months wash out

Medication/treatment	Action to be taken	Required wash-out (prior to randomization/first treatment)
Surgical or physical (such as ThermaClear™) light and laser therapy (including blue light, use of handheld devices, tanning devices or photodynamic therapy [PDT]) on area of evaluation.	To be discussed with sponsor on case by case basis.	Wash-out: 4 weeks
After baseline, use of any tanning device, or excessive exposure to sun [with intention to tan], any handheld light device to treat skin or procedures for hair removal in the evaluation areas are not permitted.		
Any live vaccines (this incl. nasal-spray flu vaccine)	Discontinue study treatment	6 weeks
Any topical for acne on area for evaluation (face, back, chest, shoulder, neck), including retinoids (such as adapalene, tazarotene, isotretinoin or tretinoin), antibacterial and antibiotics (such as benzoyl peroxide, clindamycin or erythromycin) and any other topical keratolytic or peeling agents (such as salicylic acid, or lactic acid) or any other anti-acne drug (such as dapsone, azelaic acid). These topicals include over the counter (OTC) products for acne, such as medicated emollients, medicated cleansers or medicated soaps.	To be discussed with sponsor on case by case basis for treatment period 1. In the extension period 2, topical anti-acne treatment is allowed, if needed (to be recorded as concomitant medication).	Wash out for 1 week (for OTC products) and for 2 weeks (for prescription drugs (RX)).

5.3 Dietary restrictions and smoking

In this study, no particular dietary restrictions are required. However, acne patients are recommended to follow a healthy diet, but will not receive specific dietary restrictions

5.4 Other restrictions

During the trial, all patients should avoid excessive sun bathing, including for the purpose of tanning. To avoid sunburn, appropriate sun avoidance and protection should be exercised. In particular, patients with outdoor activity should be counseled regarding appropriate sun avoidance and protection.

No procedures to reduce acne lesions are allowed, including chemical peels, laser or light procedures and surgery (see [Section 5.2](#)).

Topical products used on the area of evaluation, such as emollients, cleansers, day creams etc. used by the patient should be checked by the investigator to see if she/he can continue using it, to avoid use of any medicated anti-acne products in treatment period 1 (see [Section 4.2](#). or [Section 5.2](#)). Use of facial medium depth chemical peels (excluding home regimens) within 3 months prior to baseline are prohibited.

Planned vaccination is allowed, unless live vaccines are needed. Any live vaccines (this includes nasal-spray flu vaccine) should be initiated at least 6 weeks before baseline.

6 Treatment

6.1 Study treatment

Details on the requirements for storage and management of IMP, and instructions to be followed for subject numbering, prescribing/dispensing and taking IMP are outlined in the SOM.

6.1.1 Investigational treatment and placebo

Table 6-1 Overview of Investigational treatment

Study drug name	Formulation	Appearance	Unit dose	Packaging	Provided by
CJM112	Liquid in Vial	clear liquid	Corporate Confidential Information	Individual Patient Packs	Novartis
Placebo to CJM112	Liquid in Vial	clear liquid		Individual Patient Packs	Novartis

6.1.2 Additional study treatment

No additional treatment beyond investigational treatment and placebo are included in this trial.

6.2 Treatment arms

Overall subjects will be assigned to one of the following 3 treatment arms in a ratio of 1:1:1.

Study treatments are defined as:

- CJM112 once monthly for a total of up to 7 doses
- CJM112 once monthly for a total of up to 7 doses
- Placebo for a total of up to 3 doses, followed by re-randomization into either active treatment group for extension period 2 for a total of up to 4 active doses

Both CJM112 and placebo will be provided as liquid in vial according to the dose that is required. Placebo will be matched by volume and number of syringes/injections to maintain double-blind. Details on the study medication preparation will be provided in the Pharmacy Manual provided separately. Dosing is by s.c. administration at time points specified in the [Assessment Schedule](#).

Unbalanced randomization will be used at the start of trial to enhance early comparison of CJM112 vs placebo and interim efficacy/futility assessment. A 3:1:3 randomization

Corporate Confidential Information will be used for the first 35 patients and thereafter 1:2:1 Corporate Confidential Information for the remaining 40 patients. In case more than 75 patients are randomized to the study, the randomization ratio will be 1:1:1 after the first 75 patients.

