The primary endpoint is a comparison of facial inflammatory lesion counts at week 12, an established duration period for anti-acne treatments, but other time points will be explored. Many acne treatments, including isotretinoin, need longer treatment duration for full efficacy. However, in this moderate to severe acne population, the increased acne scarring risk in the face makes it difficult to include patients in a placebo controlled study with more than 12 weeks duration, hence, it is planned to offer placebo-treated patients to be re-randomized after 12 weeks to either the Corporate Confidential Information treatment group in extension period 2. As the placebo effect can be quite high (up to 30-40% reduction in inflammatory lesion count at week 12) and the endpoints dependent on the investigator assessment, a blinded study is deemed optimal to generate reliable data for treatment period 1, which are not influenced by investigator's perception. Extension period 2 data may be influenced by a lower severity due to a long run-in and drop-outs, but may show a similar trend. Given the high placebo effect, a parallel comparison is preferred over a cross over design.

The randomization scheme overall is planned to be 1:1:1. This ensures that groups are balanced and the interpretation of results is possibly more robust. However, unbalanced randomization will be used at the start of trial to enhance early comparison of Corporate Confidential Information vs placebo and interim efficacy/futility assessment. A 3:1:3 randomization Corporate Confidential Information will be used for the first 35 patients and thereafter 1:2:1 Corporate Confidential Information for the remaining 40 patients. In case more than 75 patients are randomized to the study, the randomization ratio will be 1:1:1 after the first 75 patients. Patients who have been randomized to placebo group in treatment period 1 and agree to continue into extension period 2 will be re-randomized into the two active dosing groups for another 12 weeks treatment, again with randomization ratio 1:1.

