3.3 Rationale for dose/regimen, route of administration and duration of treatment

Corporate Confidential Information

Corporate Confidential Information

In the present study, the dose

Corporate Confidential Information

is proposed to explore efficacy in the moderate to severe acne population, which corresponds to one dose Corporate Confidential Information administration monthly, considered as practical and feasible for this population. It is anticipated that the onset of action in acne is seen within months and well within treatment period 1 and extension period 2, thus, no loading dose during the first month was selected. In adult psoriasis patients, a cumulative dose over 12 weeks (with a loading dose over the first month) was safe and effective. This dose achieved a clear clinical reduction of the PASI75 responders (achieving a reduction of 75% over baseline in PASI score) of over 80% of the included patients in the dose group. Corporate Confidential Information

As outlined in [Section 1.3.1](#), the safety signals in the HS population versus placebo are consistent with the safety data known from other anti-IL-17A blockers and previous results in psoriasis patients. While reducing the frequency to monthly doses, Corporate Confidential Information has a reasonable chance to distribute even in typical acne lesions, such as papules, which are more superficial and smaller than nodules, where tissue distribution is assumed difficult.

To explore a preliminary dose-efficacy relationship, a lower dose regimen in this study in moderate to severe acne patients Corporate Confidential Information

is proposed. Indeed, in a previous study in psoriasis patients, Corporate Confidential Information weekly for the 1st month and then monthly for a total of 3 months, showed clear efficacy versus placebo. The dose is, thus anticipated to demonstrate potential efficacy in acne,

as the exposure should be close to the one tested in psoriasis patients. Indeed, the clinical potency difference between CJM112 and secukinumab in psoriasis is about 7-fold based on exposure, or about 4-fold based on dose, as demonstrated (preliminary modeling) in the psoriasis study. Thus, CJM112 roughly corresponds in terms of clinical potency to secukinumab, another anti-IL-17A antibody, approved in psoriasis, psoriatic arthritis and ankylosing spondylitis.

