6.3 Treatment assignment and randomization

Randomized treatment will be assigned to individual patients by way of a randomization number at the beginning of treatment period 1. At week 12 visit, patients who have been randomized to placebo group in treatment period 1 and also agree to continue in extension period 2 will again be assigned randomly to one of the two active treatment groups via a new randomization number.

The randomization number is only used to identify which treatment the patients have been randomized to receive. The Subject number assigned to a patient at screening remains the unique identifier for the patient throughout the study. For information on subject numbering, please see 'Subject numbering' section in the SOM.

Replacement randomization numbers will be in the same range of the initial randomization list. If a subject requires a replacement, the replacement subject will be assigned a randomization number corresponding to the original patient (e.g. Subject 6103 would replace Subject 5103). Any additional patients enrolled will use sequential subject numbering.

Patients who discontinued from study treatment before completion of Visit 201 assessments for reasons other than safety may be replaced by an equal number of newly enrolled patients, until sufficient number of completers per arm at week 12 is achieved ([Section 11.7](#)). Patients who discontinue from study treatment after week 12 will not be replaced. The observed dropout rate from the first 35 patients will be used to evaluate the final total recruitment needed.

The randomization numbers will be generated using the following procedure to ensure that treatment assignment is unbiased and concealed from patients and investigator staff. A subject randomization list will be produced by the Interactive Response Technology (IRT) provider using a validated system that automates the random assignment of subject numbers to randomization numbers. These randomization numbers are linked to the different treatment arms, which in turn are linked to medication numbers. A separate medication list will be produced by or under the responsibility of Novartis Drug Supply Management using a validated system that automates the random assignment of medication numbers to packs containing the investigational drug(s).

The randomization scheme for subjects will be reviewed and approved by a member of the Randomization Office.

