11.4.2 Statistical model, hypothesis, and method of analysis

The log transformed inflammatory facial lesion count is expected to be approximately normally distributed. It will be analyzed using a Bayesian mixed effect model for repeated measures (MMRM), with log transformed baseline inflammatory facial lesion count as a covariate; treatment sequence, visit, treatment group by visit interaction and log transformed baseline inflammatory facial lesion count by visit interaction as fixed effects. A non-informative prior will be utilized to obtain the posterior estimates. Unstructured covariance structure will be used. Other factors such as gender and race will also be explored for statistical significance if the distribution per factor is reasonably balanced. The log transformed baseline lesion count will be centered and standardized before used in the model.

Data up to Week 12 will be included in the model, for the comparison of CJM112 versus placebo at Week 12, which is of primary interest. Corporate Confidential Information

Bayesian posterior probabilities will be used to assess the following criteria as a guide to decision making ([Fisch et al 2015](#)), though other criteria may be taken into account:

Corporate Confidential Information

The posterior estimates of the treatment effect and the treatment difference (along with its 90% credibility interval) at each visit (with Week 12 being of primary interest) will be provided. The results will be reported in terms of ratio of geometric means by back

transforming the estimates from the log-scale. Data will also be presented in graphics such as spaghetti plot.

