7.1.3 Statistical model, assumptions and hypotheses

The log transformed inflammatory facial lesion count will be analyzed using a Bayesian model for repeated measurements. The model will include effects including log transformed baseline inflammatory facial lesion count, treatment group, visit, treatment group by visit interaction and

log transformed baseline inflammatory facial lesion count by visit interaction. A non-informative prior will be utilized to obtain the posterior estimates and an unstructured covariance will be assumed. Other factors such as gender and race may also be explored if the distribution per factor is reasonably balanced. The log transformed baseline will be centered and standardized before used in the model.

Corporate Confidential Information

The posterior estimates of the treatment effect and the treatment difference (along with its 90% credibility interval) at each visit (with Week 12 being of primary interest) will also be provided. The results will be reported in terms of ratio of geometric means by back transforming the estimates from the log-scale.

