7.1.5 Sensitivity analyses

As a sensitivity analysis, the facial inflammatory lesion count at Week 12 will be analyzed via a generalized linear model with a Poisson or negative binomial distribution, depending on the dispersion. Baseline lesion count will be used as a covariate (or offset variable) and treatment group as a factor.

The primary analysis may be repeated with Baseline defined as the mean of Screening and Visit 101.

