7.1.6 Supportive analyses

Corporate Confidential Information

Due to the nature of the primary endpoint, heterogeneity may also be observed due to different assessors and sites, hence as a supportive analysis site and/or assessor may also be included in the primary analysis model as fixed effects to investigate site/assessor impact.

Further, supportive analyses may be performed adding other covariates in the model such as baseline IGA and other baseline characteristics in the model.

Corporate Confidential Information

Corporate Confidential Information

8 Statistical methods for safety and tolerability data

All patients within the Safety analysis set will be included in the safety data analysis.

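### The allocation ratio changes after 35 patients, but no visible model term carries randomisation stage, so one dose's contrasts are partly confounded with enrolment time

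*Protocol*

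**What the plan says.** Protocol 3.2 and 6.2 aim for 1:1:1 overall but reach it in two steps. A 3:1:3 ratio "will be used for the first 35 patients and thereafter 1:2:1" for the other 40. The stated purpose is an earlier comparison of CJM112 with placebo. Protocol 3.2 adds: "In case more than 75 patients are randomized to the study, the randomization ratio will be 1:1:1 after the first 75 patients".

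Protocol 11.4.2 gives the primary Bayesian repeated-measures model the log baseline count as covariate, with "treatment sequence, visit, treatment group by visit interaction and log transformed baseline inflammatory facial lesion count by visit interaction as fixed effects". SAP 7.1.3 has treatment group where the protocol has treatment sequence: "The model will include effects including log transformed baseline inflammatory facial lesion count, treatment group, visit, treatment group by visit interaction", plus baseline by visit. For the Week-12 Poisson or negative binomial sensitivity model, SAP 7.1.5 says: "Baseline lesion count will be used as a covariate (or offset variable) and treatment group as a factor".

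Optional additions are gender and race (Protocol 11.4.2, SAP 7.1.3), baseline IGA and other baseline characteristics (SAP 7.1.6), and, also in SAP 7.1.6, site and assessor: "as a supportive analysis site and/or assessor may also be included in the primary analysis model as fixed effects". No readable section names randomisation stage, enrolment period or calendar time.

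On replacements, Protocol 6.3 says "the replacement subject will be assigned a randomization number corresponding to the original patient".

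**The concern.** Equal totals hide unequal timing. One active arm recruits mostly late, while placebo and the other active arm recruit mostly early. Suppose patients enrolled later respond differently for reasons that baseline count does not capture, such as season, site mix, rater behaviour or the size of the placebo response. A model without stage then credits part of that difference to the dose. Recruiting more patients at the same ratios would not reduce this bias.

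The order of arms in the synopsis (high, low, placebo) suggests that the affected arm is the low dose. Protocol 3.3 gives that dose's purpose: "To explore a preliminary dose-efficacy relationship, a lower dose regimen in this study". The comparison at risk is therefore the dose comparison, together with the affected dose's own contrast with placebo.

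**Working it through.** **Inputs.** Ratios and stage sizes: Protocol 6.2. SD 0.47 on the log scale, about 21 completers per arm, and a 40% effect (0.511 on the log scale): Protocol 11.7. Efficacy criteria (Protocol synopsis, data analysis): at least 90% posterior probability of being better than placebo, and at least 50% probability of an effect of 30% or more (0.357 on the log scale). The drift between stages is **assumed** to be 0.10 to 0.30 on the log scale, in either direction. All probabilities use a normal approximation with a flat prior.

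**The plan's own figures first.** With 10 per arm, SE = 0.47 × √(2/10) = 0.210. The chance of meeting both efficacy criteria is 4.5% with no effect and 76.8% at a 40% effect. Futility under no effect is 40.0%. Table 11-1 gives 5%, 77% and 40%. With 21 per arm taken as a single look, the chances are 0.7% and 85.6%. Counted as met at either look, they are 4.8% and 90.3%, which matches the table's 5% and 90%. So the second row of Table 11-1 is cumulative. The single-look figures are used below, because only 5 of the first 35 patients are in the affected arm and a 10-per-arm look cannot come from stage 1 for that dose.

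**Stage shares.**

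| | Affected dose | Other dose | Placebo |
|---|---|---|---|
| Stage 1 (35 at 3:1:3) | 5 | 15 | 15 |
| Stage 2 (40 at 1:2:1) | 20 | 10 | 10 |
| Total | 25 | 25 | 25 |
| Share in stage 1 | 20% | 60% | 60% |

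**Bias.** Bias = (20/25 − 10/25) × drift = 0.40 × drift for the affected dose versus placebo and versus the other dose. For the other dose versus placebo it is (10/25 − 10/25) × drift = 0.

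**Effect on the decision.** At 21 per arm, SE = 0.47 × √(2/21) = 0.145. The 90% criterion needs an estimate of at least 1.2816 × 0.145 = 0.186, and the 50% criterion needs at least 0.357, so 0.357 is the binding limit. With bias b:

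- No true effect, later patients improve more: 1 − Φ((0.357 − b)/0.145)
- True 40% effect, later patients improve less: 1 − Φ((0.357 − 0.511 + b)/0.145)

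| Drift | b | b as share of 0.357 | Criteria met, no effect | Criteria met, 40% effect |
|---|---|---|---|---|
| 0 | 0 | 0% | 0.7% | 86% |
| 0.10 | 0.04 | 11% | 1.4% | 78% |
| 0.20 | 0.08 | 22% | 2.8% | 70% |
| 0.30 | 0.12 | 34% | 5.1% | 59% |

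**Cost of a stage term.** Without stage, the variance factor of a contrast is 1/25 + 1/25 = 0.080. Stage adds (difference in stage share)² divided by the within-arm sum of squares of the stage indicator. That sum is 25 × (0.6 × 0.4 + 0.6 × 0.4 + 0.2 × 0.8) = 16. For the affected contrasts the addition is 0.40²/16 = 0.010, giving 0.090. The SE ratio is √(0.090/0.080) = 1.061. For the other dose versus placebo the addition is zero. With SE 0.154, the criteria are met with probability 1.0% under no effect and 84.2% at a 40% effect.

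**Simulation with a stage term** (15,000 runs per drift, 21 random completers per arm): mean bias within 0.001 of zero, 1.0% to 1.1% under no effect, and 83.9% to 84.7% at a 40% effect, at every drift.

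**Dilution of the 0.40.** If 15% of stage-1 patients in each arm are replaced by later enrolees, the late shares are (20 + 0.75)/25 = 0.83 and (10 + 2.25)/25 = 0.49, a difference of 0.34. With 15 extra patients at 1:1:1 the stage-1 shares are 15/30 and 5/30, a difference of 0.33.

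**The case against.** - **Redaction.** Confidential blocks follow the model text in both documents, and the SAP's wording does not close the list of effects. A stage term could sit in hidden text, and the dose label at each ratio position is hidden too. This stands, and it limits the claim to what is visible.
- **Drift is assumed.** Nothing in the documents reports drift. The protocol puts the placebo reduction at 20-30% (3.7) and at up to 30-40% (3.2). The whole span from 20% to 40% is ln(0.8/0.6) = 0.288, so a drift of 0.30 is an upper bound and not an expectation. This stands. The 5.1% at that bound is close to the 5% in Table 11-1, but that figure accumulates over two looks, whereas the single-look figure for the affected dose is 0.7%.
- **Small drift does not repay the term.** The added variance is 0.47² × (2/21) × 0.125 = 0.0026. Squared bias, 0.16 × drift², exceeds this only when drift is above about 0.13. With smaller drift the adjusted estimate has a slightly larger mean squared error. This is true, but the loss is small and known in advance, while the bias is neither known nor bounded.
- **Partial cover exists.** Evaluator training, keeping the same evaluator, blinding, and the optional site, assessor and baseline covariates may absorb some drift. All the covariates are optional and none targets stage or season.
- **Low stakes.** The trial is non-confirmatory, its criteria only guide decisions, and the prioritised dose versus placebo is balanced by stage. This stands and sets the weight of the point.

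**Conclusion.** The point holds as a cheap improvement and not as a flaw in the main comparison. Allocation probability depends on stage, and no visible analysis conditions on it. The affected dose's contrasts with placebo and with the other dose carry a bias of 0.40 times any additive drift not explained by baseline count, or about 0.33 to 0.34 with the replacements or extra patients considered above. The confounding is partial, because every arm recruits in both stages. With no drift there is no bias.

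The decision probabilities rest on an assumed drift of 0.10 to 0.30, SD 0.47, 21 completers per arm and a single look. That the affected arm is the low dose is an inference from arm order.

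**What to change.** Before unblinding, confirm whether redacted text already contains a stage term. If not, amend the SAP:

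- Add randomisation stage and stage by visit as fixed effects in the primary Bayesian model, and stage as a factor in the Week-12 count model. Define stage by the ratio in force on the date the patient was actually randomised.
- Code a replacement by the replacement's own randomisation date. Repeat the analysis once with the original patient's stage.
- Merge 1:1:1 patients beyond 75 with stage 2 if that level is sparse, for example fewer than 5 in any arm.
- Drop the term at any look that contains stage-1 patients only.

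**Cost.** A two-level factor with its visit interaction in the primary model, the factor alone in the count model, one coding rule and one repeat analysis. The SE of the affected contrasts rises by about 6%. With 3 to 15 patients beyond 75, the rise is 5.8% to 5.0% with a third level, or 5.6% to 4.3% if merged. Single-look power goes from 86% to 84%, and the no-drift chance of a false go from 0.7% to 1.0%. The other dose versus placebo is unchanged. The term removes additive drift only. It does not address a treatment effect that itself differs between stages.
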